Study Protocol and Statistical Analysis Plan (SAP) — Frailty Evaluation Component

1. Administrative information

Study title (short): FRAGSALUD — educational programme for frail/pre-frail older adults.

ClinicalTrials.gov Identifier: NCT05610605.

Study period: Conducted March 2022 – September 2023; assessments at baseline, 6 months (end of intervention), and 12 months (6 months post-intervention).

Primary SAP scope: frailty phenotype (Fried criteria) — score, categorical status (robust / pre-frail / frail).

Document date: 24/09/2025

2. Background & rationale (frailty)

Frailty is a state of increased vulnerability to stressors reflecting reduced physiological reserve. The study tested whether a 6-month educational intervention changes frailty status and frailty score compared with usual care in community-dwelling older adults with at least one Fried criterion.

3. Objectives (frailty component)

Primary frailty objective: Evaluate the effect of the 6-month educational programme on the Fried frailty total score at 6 months (end of intervention) and at 12 months (6 months post-intervention), compared with control.

Secondary frailty objectives:

- Evaluate shifts in frailty categories (robust / pre-frail / frail) between baseline, 6 months and 12 months.

4. Study design (brief)

Multicentre, parallel-group randomised controlled trial; participants randomised to educational programme or control (usual care). Assessments at baseline, 6 months, and 12 months.

5. Population and eligibility

Inclusion: Community-dwelling adults aged ≥ 65 years with ≥ 1 Fried frailty criterion (pre-frail or frail).

Exclusion: Institutionalised individuals; robust participants (zero Fried criteria).

Final analysed sample: 199 participants (109 intervention, 90 control after attrition).

6. Frailty measurement (operational definition)

Frailty was operationalised using the Fried physical frailty phenotype, consisting of:

- Shrinking (unintentional weight loss ≥ 4.5 kg or $\geq 5\%$ in past year).
- Weakness (sex- and BMI-specific grip strength cut-offs).
- Poor endurance/exhaustion (self-reported ≥ 3 days in previous week).
- Slowness (4-m timed walk with sex- and height-specific cut-offs).
- Low physical activity (Minnesota Leisure Time Physical Activity Questionnaire).

Scoring: 0–5. Categories: robust = 0; pre-frail = 1–2; frail ≥ 3 .

7. Outcomes (frailty-specific)

Primary frailty outcome: Change in Fried total score from baseline to 6 months and 12 months.

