Secondary frailty outcomes:

- Proportion of participants in each frailty category at each timepoint.

8. Sample size

Target ≥ 196 participants, based on effect size 0.5 SD, $\alpha = 0.05$, power = 80%, allowing for 15% dropout.

9. Randomisation and allocation

Computerised block randomisation ensuring balance between groups.

10. Blinding

Participants and intervention deliverers were not blinded. Outcome assessors and analysts were blinded where possible.

11. Data collection schedule

Baseline: Fried components.

6 months: repeat assessments.

12 months: repeat assessments.

12. Statistical Analysis Plan

Analysis populations: Intention-to-treat and per-protocol (sensitivity).

Primary analysis: Linear mixed-effects model with Fried score as dependent variable; fixed effects for group, time, and group \times time; random effect for participant; adjusted for age, sex, education.

Secondary analysis: Frailty category transitions using chi-square, logistic regression, or multinomial models.

Sensitivity analyses: per-protocol, alternative frailty scoring, responder definitions.

13. Reporting and tables/figures

Baseline frailty table by arm.

Adjusted change table with β (95% CI) and p-values.

Frailty category transitions figure.

14. Key frailty results

At 6 months, intervention group reduced Fried score by -0.60 vs -0.015 in controls ($\beta = -0.515$, $p = 0.007$).

At 12 months, $\beta = -0.714$, $p < 0.001$.

Frailty category improved in intervention group: increase in robust participants, reduction in frail participants.

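### The primary model has no term for shared programme deliverers, so the precision of the 6- and 12-month effects is untested against clustering in the programme arm

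*Combined protocol and SAP*

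**What the plan says.** Section 4 describes a multicentre trial with individual randomisation to an educational programme or usual care. Section 10 states "Participants and intervention deliverers were not blinded", so the programme arm had deliverers, in the plural. The document does not say how many there were, how many participants each served, whether a participant had one or several, or whether sessions were individual or in groups. It does not describe usual care beyond the name.

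The primary model in section 12 has fixed effects for group, time and their interaction, with "random effect for participant; adjusted for age, sex, education". It has no deliverer, class or centre term and no robust variance. The three sensitivity analyses listed there concern the analysis set, the frailty scoring and the responder definition; none concerns shared delivery. Section 8 gives "Target ≥ 196 participants, based on effect size 0.5 SD" and "power = 80%, allowing for 15% dropout", with no design effect or ICC. Section 5 gives 109 programme and 90 control participants analysed. Section 14 reports β = -0.515 (p = 0.007) at 6 months and β = -0.714 (p < 0.001) at 12 months.

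**The concern.** A participant random effect handles the correlation among one person's repeated scores. It does nothing for correlation between people. If those taught by the same educator tend to change alike, that shared variation arises after baseline and in the programme arm. It therefore enters the group-by-time contrast, and the stated model has nowhere to put it.

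The precision of both primary time points is at stake. Section 13 commits to 95% confidence intervals and p-values for the adjusted changes, and these rest on an independence assumption that the plan neither states nor tests. If deliverers differ, the intervals describe the programme as given by these particular educators and are too narrow as a statement about the programme in general.

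**Working it through.** **Inputs from the document.** 109 programme and 90 control participants (section 5); β = -0.515, p = 0.007 at 6 months and p < 0.001 at 12 months (section 14); 0.5 SD, alpha 0.05, 80% power and 15% dropout (section 8).

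**Assumed inputs.** m, the number of programme participants per deliverer (or class), and the ICC of change in Fried score within deliverer. The document gives neither, so a range is shown. Clustering is placed in the programme arm only.

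**The plan's sample size.** Two-sided, 1:1: 2 x (1.960 + 0.842)² / 0.5² = 62.8, so 63 per arm, 126 in total, and 126/0.85 = 149 after dropout. The stated 196 is not reproduced at 80% power. It does match 90% power: 85 per arm, 170 x 1.15 = 196. This is a separate matter. It means there is spare power, but a larger sample does not repair a standard error that omits a source of variation.

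**Implied 6-month precision under independence.** z for p = 0.007 is 2.697, so SE = 0.515/2.697 = 0.191, with a 95% CI of about -0.89 to -0.14.

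**Effect of clustering.**
- Design effect in the programme arm: DE = 1 + (m-1) x ICC.
- SE ratio: R = sqrt[(DE/109 + 1/90) / (1/109 + 1/90)].
- Adjusted 6-month p: two-sided, from z = 2.697/R.

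For example, with m=10 and ICC 0.05: DE = 1.45; R = sqrt(0.02441/0.02029) = 1.10; z = 2.697/1.097 = 2.46; p = 0.014.

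| m | ICC | DE | SE ratio | 6-month SE | 6-month p |
|---|---|---|---|---|---|
| 6 | 0.02 | 1.10 | 1.02 | 0.195 | 0.008 |
| 10 | 0.05 | 1.45 | 1.10 | 0.209 | 0.014 |
| 15 | 0.10 | 2.40 | 1.28 | 0.244 | 0.035 |
| 27 | 0.10 | 3.60 | 1.48 | 0.282 | 0.068 |

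The last row corresponds to about four deliverers (109/4 = 27).

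**Break-even.** The 6-month p reaches 0.05 when R = 2.697/1.960 = 1.376. Then DE = [1.376² x (1/109 + 1/90) - 1/90] x 109 = 2.98, so (m-1) x ICC is about 2: ICC 0.22 at m=10, 0.10 at m=20, 0.037 at m=55. At 12 months, taking p as just under 0.001 (z = 3.291), R must reach 1.679, which needs DE of about 5.0.

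**Type I error.** With nominal 5%, the actual rate is 2 x P(Z > 1.96/R): 7.4% at m=10, ICC 0.05 and 12.5% at m=15, ICC 0.10. These rates belong to a null of zero average effect with real variation between deliverers.

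**Limits of the calculation.** It applies a formula for two independent means to the change contrast and uses a normal approximation. With few deliverers, small-sample degrees of freedom would widen the interval further.

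**The case against.** The strongest objection is that the nesting is not documented. It rests on one plural noun in the blinding section. If one deliverer taught everyone, or several deliverers taught each participant, there are no separate deliverer clusters and the extra term could not be specified. Group classes are only a possibility. This stands, and it is why the point is conditional.

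A reader might infer that usual care has no shared layer at all. The document does not describe usual care, and controls may share clinicians within centres. Programme-only clustering is an assumption of the calculation.

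A reader might also infer that the stated alpha of 0.05 is simply not held. That goes too far. Under the null that the programme affects no one, individually randomised participants have no deliverer effect to share, and this mechanism causes no inflation. The inflated rates need the weaker null given above. Whether to generalise beyond the deliverers used is a choice of inferential target.

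Finally, centre is the one higher grouping that the document does state, and it is missing from the model too. With one deliverer per centre, deliverer and centre cannot be separated in the programme arm, and a centre-by-arm term would capture the same variation. Where a centre had several deliverers or classes, a centre term would not be enough.

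None of this removes the gap: the model and its sensitivity analyses leave independence within the programme arm untested.

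**Conclusion.** The point holds as a conditional one. Any positive within-deliverer correlation of change makes the group-by-time SEs at 6 and 12 months too small under the stated model, while β is little affected. Over the range shown, the SE understatement runs from negligible (2%) to substantial (48%).

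The document supports neither of two firmer conclusions that a reader might draw. One is that the 6-month result fails: it does so only if (m-1) x ICC exceeds about 2. The other is that it survives: that depends on where the assumed range stops, since p is 0.035 at m=15 and 0.068 at m=27 with the same ICC of 0.10. The 12-month result is more robust. Because m, the ICC and the delivery format are all missing, this is an inexpensive improvement to the analysis and not a demonstrated error in the reported results.

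**What to change.** Keep the stated primary model. Add to the section 12 sensitivity analyses, labelled as added after the results were known, a partially nested model with:
- a random effect for deliverer (or for class, if sessions were in groups), applied to programme participants at 6 and 12 months only;
- each control as a singleton;
- a small-sample degrees-of-freedom correction.

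Report its β, 95% CI and p-value beside the primary result at both time points, and state the delivery format, the number of deliverers and the participants per deliverer. If there was one deliverer per centre, use a centre-by-arm term instead. If deliverers were crossed with participants, or a single one served everyone, state that the term cannot be estimated.

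The cost is SAP wording, one further model fit and linkage of each programme participant to a deliverer or class. The document does not say whether records for that exist. No new outcome data are needed. With few deliverers the interval may widen more than slightly, and a variance estimate of zero would be weak evidence that there was no clustering.

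### The primary model states only a participant random effect, so the 6- and 12-month contrasts share one standard error; name the covariance structure and report an unstructured refit

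*Combined protocol and SAP*

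**What the plan says.** Section 12 of the combined protocol and SAP gives the primary analysis as "Linear mixed-effects model with Fried score as dependent variable; fixed effects for group, time, and group" by time, with "random effect for participant; adjusted for age, sex, education". Baseline is therefore one of the modelled outcomes. The section names no random slope, residual covariance structure, visit-specific variance or robust standard error. None of its sensitivity analyses (per-protocol, alternative scoring, responder definitions) varies the covariance.

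Section 4 fixes three visits: "Assessments at baseline, 6 months, and 12 months". Section 7 makes change to both follow-up visits the primary outcome, and Section 13 promises a confidence interval and p-value for adjusted change.

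Section 5 admits adults "with ≥ 1 Fried frailty criterion (pre-frail or frail" and excludes "robust participants (zero Fried criteria". Section 6 lets the score reach 0 at any visit: "Scoring: 0–5. Categories: robust = 0; pre-frail = 1–2". Section 14 reports that more intervention participants were robust after baseline, so scores of 0 did occur at follow-up.

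**The concern.** A random intercept with one residual variance assumes equal variance at each visit and equal correlation between any two visits (compound symmetry). There are two reasons to doubt this here. The entry rule cuts off the bottom of the baseline distribution but not of the later ones. And scores 12 months apart may correlate less than scores 6 months apart, particularly as the last visit falls 6 months after the intervention ended.

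The model pools one residual variance over all pairs of visits and uses it for both primary contrasts. If the change to 6 months and the change to 12 months have different variances, one standard error cannot be right for both. At stake are the width of the two primary confidence intervals and the error rate of the two primary tests. If some records are incomplete, a wrong covariance can also shift the estimates; the documents do not allow that to be sized.

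**Working it through.** **Inputs from the documents.** Three visits; 199 analysed (109 and 90); entry score at least 1; score range 0–5; 6-month β = −0.515 with p = 0.007; 12-month β = −0.714 with p < 0.001. No SD, between-visit correlation or standard error is given, so there is no figure in the plan to reproduce. The SDs and correlations below are assumptions. Time is taken as categorical (Section 14 gives a separate β for each visit), data as complete, and tests as two-sided at 5%.

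**Formula.** Let D01, D02 and D12 be the variances of the within-person differences for 0–6, 0–12 and 6–12 months, for example D01 = s0² + s1² − 2·r01·s0·s1. With complete data the random-intercept model gives both contrasts a variance proportional to the mean M = (D01 + D02 + D12)/3. The true variances are proportional to D01 at 6 months and D02 at 12 months. So:

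- model SE / true SE = √(M/D01) at 6 months and √(M/D02) at 12 months
- actual α = 2·[1 − Φ(1.96 × ratio)]

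**Step 1: entry rule alone.** Take SDs of 0.9, 1.2, 1.2 and all correlations 0.5.

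- D01 = D02 = 0.81 + 1.44 − 1.08 = 1.17
- D12 = 2.88 − 1.44 = 1.44
- M = 3.78/3 = 1.26
- Both ratios = √(1.26/1.17) = 1.04, so actual α is about 4.2% at both visits

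The compressed baseline is shared by both contrasts, so both standard errors move together.

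**Step 2: decay alone.** Take equal SDs of 1 and correlations of 0.7 (0–6), 0.7 (6–12) and 0.49 (0–12), which is full autoregressive decay.

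- D01 = D12 = 2 − 1.4 = 0.60
- D02 = 2 − 0.98 = 1.02
- M = 2.22/3 = 0.74
- 6 months: √(0.74/0.60) = 1.111, actual α about 3.0%
- 12 months: √(0.74/1.02) = 0.852, actual α about 9.5%

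**Step 3: other assumed cases.**

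| SDs (0, 6, 12 months) | r 0–6 / 6–12 / 0–12 | Ratio at 6 | Ratio at 12 |
|---|---|---|---|
| 0.8, 1, 1 | 0.6 / 0.6 / 0.6 | 1.03 | 1.03 |
| 0.8, 1, 1 | 0.45 / 0.65 / 0.45 | 0.96 | 0.96 |
| 0.8, 1, 1 | 0.5 / 0.65 / 0.45 | 0.99 | 0.94 |
| 0.9, 1.2, 1.2 | 0.5 / 0.65 / 0.4 | 1.01 | 0.93 |
| 0.8, 1, 1 | 0.65 / 0.65 / 0.50 | 1.09 | 0.92 |
| 0.8, 0.95, 1.1 | 0.65 / 0.65 / 0.50 | 1.17 | 0.89 |

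Random-intercept models fitted to simulated data with arms of 109 and 90 (150 runs per case) agreed with the formula for the first, second and fifth rows.

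**Step 4: a score shaped like this one.** Five correlated yes/no items were summed to a 0–5 count, keeping only people with a baseline count of at least 1 (item prevalence 0.2 to 0.5). Baseline SD was about 0.80–0.91 of the follow-up SD, for example 0.98 against 1.22.

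- With no decay, the ratios were 1.01–1.02 at both visits.
- With latent visit-to-visit correlation of 0.9 to 0.7, they were 1.03–1.05 at 6 months and 0.95–0.98 at 12 months. Actual α was about 4.0–4.4% and 5.4–6.3%.

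**Step 5: margin in the reported results.** At 6 months p = 0.007 corresponds to z = 2.697, so z falls below 1.96 only if the ratio is under 1.96/2.697 = 0.73. At 12 months p < 0.001 means z above 3.29, so the ratio would have to be under 1.96/3.29 = 0.60. The lowest ratios found above are 0.96 and 0.85. This holds the estimates fixed and takes the reported p-values as coming from the Section 12 model.

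**The case against.** The strongest reply is that nothing in the documents shows an error of any particular size or direction. That stands. The plan also says only that there is a participant random effect, so compound symmetry is the plain reading rather than an explicit choice. If another structure was used, the gap is that it was not stated.

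A reader might infer that the entry rule makes the two standard errors wrong in opposite directions. The documents do not support this. Truncation at entry acts on the baseline that both contrasts share, so alone it moves both the same way. Opposite errors need correlation that decays with time, or variance that rises from 6 to 12 months. With either, they appear without any entry rule (Step 2). Even with some decay, both standard errors can be too small (0.99 and 0.94).

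A reader might also want to recompute the reported p-values. That is not possible from the documents. The 12-month standard error is not reported; p < 0.001 only bounds it below 0.714/3.29 = 0.217. The complete-data formula may not apply either. With complete data and covariates that do not change over time, the 6-month contrast would equal the raw difference in change, −0.60 − (−0.015) = −0.585, but Section 14 gives −0.515. Incomplete records, or a different model or contrast, must lie behind the reported figure.

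Finally, the study ran to September 2023, the document is dated 24/09/2025, and it contains results. Changing the primary model now would be post hoc. That shapes the remedy but does not remove the need for it.

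**Conclusion.** The concern holds as a modest specification weakness. On the plain reading, Section 12 imposes equal variance and equal correlation and, with complete data, gives both primary contrasts one standard error. Equal variance is doubtful by design. The entry rule alone shifts both standard errors by about 1–4% in the same direction: upwards when correlations are equal, downwards if the correlations with baseline are clearly lower than that between the two follow-up visits.

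If correlation also decays, the 6-month standard error can be too large by roughly 3–5% and the 12-month one too small by 2–5% in truncated-count simulations, and by about 11% and 15% under 0.7/0.7/0.49. One assumed case that adds rising SDs reaches 17% at 6 months. All of this rests on assumed SDs and correlations, complete data and categorical time.

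The margins in Step 5 suggest that the reported conclusions would probably not change. The remedy does not depend on which covariance is true.

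**What to change.** In Section 12, specify time as categorical with an unstructured within-participant covariance over the three visits, fitted by REML with Kenward-Roger degrees of freedom. Keep the 6- and 12-month group-by-time contrasts as the primary estimates. The alternative is to keep the random intercept and report robust (sandwich) standard errors. This repairs the standard errors but does not change how incomplete records are weighted, so the unstructured model is preferable if visits are missing.

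Because Section 14 already gives results, the document should state which structure produced them. The sponsor should then refit with the unstructured covariance and report both sets of estimates, intervals and p-values, with the refit labelled post hoc.

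The cost is one additional analysis and four extra covariance parameters (six instead of two), which 199 participants support easily.

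### Section 14 gives the category result as a direction of change in the intervention arm alone, so it does not answer the between-arm question on frailty status that section 2 poses

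*Combined protocol and SAP*

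**What the plan says.** Section 2 of the combined protocol and SAP states that the trial tested "whether a 6-month educational intervention changes frailty status and frailty score compared with usual care". Status is therefore part of the between-arm question, alongside the score.

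The category outcome then appears as follows:

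- Section 3, secondary objective: "Evaluate shifts in frailty categories (robust / pre-frail / frail) between baseline, 6 months and 12 months". The primary (score) objective just above it ends "at 12 months (6 months post-intervention), compared with control".
- Section 7, secondary outcome: "Proportion of participants in each frailty category at each timepoint".
- Section 12, secondary analysis: "Frailty category transitions using chi-square, logistic regression, or multinomial models".
- Section 13: a figure of category transitions is planned.
- Section 14, result: "Frailty category improved in intervention group: increase in robust participants, reduction in frail participants".

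On entry, section 5 requires at least one Fried criterion and excludes robust people. Section 6 defines robust as a score of 0. Section 5 gives the analysed sample as 109 intervention and 90 control participants.

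Section 14 treats the score differently. It gives a 6-month control change (-0.015, against -0.60 in the intervention arm) and between-arm coefficients with p-values at both follow-up visits.

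**The concern.** The category result in section 14 has no counts, percentages, control-arm figure, between-arm estimate, confidence interval, p-value or visit. Section 12 lists three kinds of analysis for categories, and no result from any of them is reported.

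In a randomised trial, a reader may take a sentence placed under key results as an effect of the programme on frailty status. A change within one arm cannot show that. The robust half is especially weak, because the entry rule fixes its starting point at the bottom of the scale: movement can go in one direction only, in either arm. At stake is whether the trial has an answer on a secondary outcome that section 7 lists separately from the score.

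**Working it through.** The document gives no category figure for either arm, so there is no stated number to reproduce. The check is one step of logic followed by illustrations whose assumed inputs are marked.

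**1. Baseline robust share.** Entry requires a score of 1 or more (section 5), and robust means a score of 0 (section 6). The share is therefore 0/109 and 0/90 in the analysed sample, provided that eligibility and baseline scoring use the same assessment and no ineligible person entered. From 0% it can only stay or rise. This step needs no model.

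**2. How easily the robust statement comes true.** It needs one person with a score of 0. If each person independently has chance q of scoring 0 at follow-up (q is assumed; the document gives none), the probability is 1 - (1 - q)^n.

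| Assumed q | n = 109 | n = 90 |
|---|---|---|
| 1% | 1 - 0.99^109 = 66.6% | 1 - 0.99^90 = 59.5% |
| 5% | 1 - 0.95^109 = 99.6% | 1 - 0.95^90 = 99.0% |

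**3. Does the small control change in score rule out a rise in robust controls?** Taking -0.015 as the 6-month mean over all 90 controls, the net change is 90 x (-0.015) = -1.35 points. If ten controls moved from 1 to 0 (10/90 = 11% robust), they contribute -10 points. Worsening of 10 - 1.35 = 8.65 points among the other controls gives the same mean. So a near-zero mean does not fix the control categories. The 12-month control change is not given.

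**4. What the intervention-arm sentence is compatible with.** Assume 22/109 = 20.2% robust in the intervention arm and vary the control count c. The difference is d = 22/109 - c/90, with Wald 95% CI d ± 1.96 x sqrt[p1(1 - p1)/109 + p2(1 - p2)/90] and an uncorrected chi-square p-value.

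| Assumed control robust | Difference, points (95% CI) | p |
|---|---|---|
| 0/90 | 20.2 (12.6 to 27.7) | <0.001 |
| 5/90 | 14.6 (5.7 to 23.5) | 0.003 |
| 9/90 | 10.2 (0.4 to 19.9) | 0.049 |
| 14/90 | 4.6 (-6.0 to 15.3) | 0.40 |
| 18/90 | 0.2 (-11.0 to 11.4) | 0.97 |

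In every row the robust share rose in the intervention arm. The between-arm answer runs from a clear difference to none.

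**5. The frail half.** Frail means a score of 3 or more. Eligibility does not set that share to zero at baseline, so it can move either way, and a reported fall carries some information. It still has no control figure beside it.

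**6. Precision available.** The unadjusted 95% half-width at a common share p is 1.96 x sqrt[p(1 - p)(1/109 + 1/90)] = 0.279 x sqrt[p(1 - p)]. For assumed p of 5, 10 and 15% this is 6.1, 8.4 and 10.0 points; for 20, 30, 40 and 50% it is 11.2, 12.8, 13.7 and 14.0 points.

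**The case against.** The best defence is that this is a gap in a short summary and not a false statement. The sentence confines itself to the intervention arm, gives no p-value and does not attribute the change to the programme. Section 13 plans a transitions figure whose content is not in this document, so control figures may exist elsewhere. All of that stands, and it limits the point to what section 14 can support.

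It is also fair to say that the whole sentence is less empty than its robust half. In a simulation of five correlated criteria with no programme effect and mean change set to -0.015 (assumed criterion prevalence 25 to 45%, between-criterion correlation 0.2 to 0.4, retest reliability 0.6 to 0.9), both halves came true together in only about 9 to 34% of arms of 109. That does not replace a comparison: the inputs are assumed, and the size of either change is not reported.

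Three stronger readings are tempting, and the documents do not support them:

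- A reader might infer that the control arm must also have gained robust participants. Only the floor is certain. At an assumed 1% chance per person, a rise occurs in about 60% of arms of 90, and the documents give no figure from which to fix that chance.
- A reader might infer from the missing mention of control in the section 3 category objective, or of arms in the section 13 figure, that no between-arm category analysis was planned. In a parallel-group randomised trial with the section 2 question and the section 12 models, a between-arm comparison is the natural reading.
- A reader might infer inflated false positives from the choice among category tests in section 12. No category test is reported, so there is no such result to discount.

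**Conclusion.** The point holds for the section 14 category sentence. Section 2 asks a between-arm question on status, and section 14 answers with a within-arm direction of change, so the sentence cannot support an effect on frailty status. The robust half can be true with or without an effect, because the share starts at 0% by eligibility. The frail half is not forced, but it cannot be judged without the control arm.

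The true between-arm difference cannot be computed from this document. The 0% floor rests on sections 5 and 6 having been applied without exception; the probabilities and example differences rest on the assumed inputs shown.

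The scope is one secondary outcome. The between-arm score coefficients (-0.515 at 6 months, -0.714 at 12 months) are not affected. Nor does this suggest that the programme failed to change status, which a reader might infer: the document does not show it either way. The sentence should be corrected, because the remedy uses existing data and could change the conclusion on status.

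**What to change.** Replace the category sentence in section 14 with:

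1. Observed counts and percentages of robust, pre-frail and frail participants in both arms at baseline, 6 and 12 months.
2. A between-arm estimate with 95% CI at each follow-up visit, from one of the models section 12 already lists.

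Draw the section 13 transitions figure by arm. Because this document is dated 24/09/2025 and already contains results, describe the choice of category contrast as not shown to be prespecified.

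If no between-arm estimate is given, label the sentence as descriptive and within-arm, and report the observed baseline robust count beside it.

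The cost is one table, one model on existing data, a redrawn figure and a few lines of text. The downside is that the category claim may become less favourable or inconclusive: with 109 and 90 participants, the unadjusted half-width of about 6 to 14 points (assumed shares of 5 to 50%) leaves room for a modest difference to be unclear.
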